### 6.2.9 ECG

A standard 12-lead ECG will be performed using local standard procedures as defined in Schedule of Events. Additional ECGs will be obtained if clinically indicated. Triplicate ECGs will be performed to confirm the significant changes of single ECG. Clinically significant abnormal findings should be recorded as an adverse event.

### 6.3 Eastern Cooperative Oncology Group (ECOG) Performance Status

The investigator/qualified designee will assess ECOG status (see [Appendix A](#)) at screening; prior to the administration of each dose of trial treatment and discontinuation of trial treatment as specified in the Schedule of Event.

#### **6.4 Radiological Evaluation**

Initial disease assessment by tumor imaging (baseline scan) must be performed within 28 days prior to the first dose of trial treatment. The site study team must review pre-trial images to confirm the subject has measurable disease as defined in the inclusion criteria. Disease assessments or scans performed as part of routine clinical management are acceptable for use as the screening scan if they are of diagnostic quality and performed within 28 days prior to the first dose of trial treatment. The CT/ PET/PET-CT should be done throughout the study at local imaging centre at time-points designated in Schedule of Events.

#### **6.5 Trial Treatment Period**

Patients will visit the study center bi-weekly for the first three cycles and thereafter every month. All visits should occur as close as possible to the protocol specified time. Complete listings of the assessments that will be performed at each visit during the trial treatment period are specified in **Table 1**.

Trial treatment period is of 8 cycles. Assessments will be performed thereafter if warranted, at the discretion of PI. Patients with progressive disease or unacceptable toxicity should be discontinued from the trial; patients with stable disease or response to therapy will continue treatment. The assessments to be performed are specified in **Table 1**.

#### **6.6 Treatment Beyond Cycle 8 (Cycle 9 onward up to Cycle 26)**

Post cycle 8, all visits will occur monthly in responding patients. During these monthly visits, Tenalisib will be dispensed, medication compliance will be monitored. Safety and efficacy assessments will be done as mentioned below. An EOT visit will be performed within 14 days after treatment ends.

- **Safety assessments:** Safety assessment will be done during the monthly visits and AEs will be reported as required by the protocol. There is no specific safety labs or evaluations to be done as per protocol. As part Standard of care, laboratory evaluations will be done and recorded per Investigator's discretion. Adverse events (AEs, SAEs and deaths) will be recorded and reported for 30 calendar days after discontinuation or completion of protocol-specific treatment. After the 30 day reporting period, only AEs, SAEs, or deaths assessed by the investigator as treatment related are to be reported.
- **Efficacy assessments:** Disease assessments should be performed at 12 weekly intervals ( $\pm$  7 days), and/ or at the EOT. For example, the appropriate radiological investigation (e.g. CT scan, PET-CT/ PET) will be performed patients at C11D1, C14D1, C17D1, C20D1, etc.
- **Drug dispensing:** Patients will be given 30 days of drug supply at the beginning of each cycle.

#### **6.7 End of Trial Treatment (EOT)**

Patients are permitted to continue treatment with Tenalisib until disease progression, or the patient is discontinued due to unacceptable toxicity or decision to discontinue treatment by the patient or the trial physician. Follow-up evaluations required after treatment ends are specified in **Table 1**.

All patients who discontinue study drugs will have an End of Treatment visit within 14 days from the last dose of study drug. If treatment is discontinued because of toxicity or any other reason(s)

at a treatment visit and no trial treatment is administered, that visit may fulfill the End of Trial Treatment Visit.

### **6.8 End of Study (EOS)**

All patients must be followed for adverse events for 30 calendar days after the last dose of study drug. A telephonic follow up is acceptable. In case of drug related AEs, further safety assessments will be performed as warranted, at the discretion of PI. The patient will be followed till resolution or stabilization of related adverse event.

### **6.9 Early Patient Termination / Patient Withdrawal**

Patients who discontinue treatment early due to disease progression or withdrawal will be asked to have all end-of-treatment safety evaluations performed as described in the protocol (see *Table 1*).

## **7 ASSESSMENT OF SAFETY**

### **7.1 Adverse Events**

The PI is responsible for collecting and reporting adverse events (see *Section 7.1.2*). It is Sponsor responsibility to report relevant SAEs to the applicable regulatory body.

#### **7.1.1 Definitions of adverse events**

Any untoward medical occurrence in a patient or clinical investigation subject administered a pharmaceutical product and which does not necessarily have a causal relationship with this treatment. An adverse event (AE) can therefore be any unfavourable and unintended sign (including an abnormal laboratory finding), symptom, or disease temporally associated with the use of an investigational product, whether or not related to the investigational product.

#### **7.1.2 Recording of adverse events**

All adverse events of any patient during the course of the trial will be reported in the case report form, and the investigator will give his or her opinion as to the relationship of the adverse event to trial drug treatment (i.e., whether the event is related or unrelated to trial drug administration). If the adverse event is serious, it should be reported immediately to Sponsor. Other untoward events occurring in the framework of a clinical trial are also to be recorded as AEs (i.e., AEs that occur prior to assignment of trial treatment that are related to a protocol-mandated intervention, including invasive procedures such as biopsies, medication washout, or no treatment run-in).

All AEs regardless of seriousness or relationship to Tenalisib, spanning from the informed consent drug until 30 calendar days after the last dose of study drug, discontinuation or completion of protocol-specific treatment as defined by the protocol for that patient, are to be recorded in the electronic Case Record Form (CRF).

#### **7.1.3 Handling of adverse events**

All adverse events resulting in discontinuation from the trial should be followed until resolution or stabilization. Patients must be followed for AEs for 30 calendar days after the last dose of study treatment. All new AEs occurring during this period must be reported and followed until resolution unless, in the opinion of the investigator, the adverse event or laboratory abnormality/ies are not likely to improve because of the underlying disease. In this case, the investigators must record his

or her reasoning for this decision in the patient's medical record and as a comment on the CRF. After 30 days of completion of protocol-specific treatment or discontinuation, only AEs, SAEs, or deaths assessed by the investigator as treatment related are to be reported.

## 7.2 Adverse Event/Serious Adverse Event Causality Assessment

Causality is assessing the relationship of the trial treatment to the adverse event. For this study, the causality assessment will be categorized as related and not related.

- **Related:** All toxicities should be considered to be related to Tenalisib unless there is a clear alternative explanation.
- **Not related:** If there is no temporal association, or another etiology has been identified as the cause, or the trial treatment cannot be implicated based upon the current information.

## 7.3 Serious Adverse Events

### 7.3.1 Definitions of serious adverse events

The definitions of serious adverse events (SAEs) are given below. The principal investigator is responsible for ensuring that all staff involved in the trial is familiar with the content of this section.

An SAE or reaction is defined as any untoward medical occurrence that: results in death, is immediately life-threatening, requires at least a 24-hour in-patient hospitalization or prolongation of existing hospitalization, results in persistent or significant disability/incapacity, or is a congenital anomaly/birth defect.

The definition of SAE also includes any important medical event. Medical and scientific judgment should be exercised in deciding whether expedited reporting is appropriate in other situations, such as important medical events that may not be immediately life-threatening or result in death or hospitalization, but may jeopardize the patient or may require intervention to prevent one of the other outcomes listed in the previous definition. These should also usually be considered serious. Examples of such events are intensive treatment in an emergency room or at home for allergic bronchospasm; blood dyscrasias or convulsions that do not result in hospitalization; or development of drug dependency or drug abuse. ***Progression of malignancy (including fatal outcomes), if documented by use of appropriate method (e.g. CT/PET) or clinically confirmed, should not be reported as a serious adverse event.***

Treatment within or admission to the following facilities is not considered to meet the criteria of "in-patient hospitalization" (although if any other SAE criteria are met, the event must still be treated as an SAE and immediately reported):

- Emergency Department or Emergency Room
- Outpatient or same-day surgery units
- Observation or short-stay unit
- Rehabilitation facility
- Hospice or skilled nursing facility
- Nursing homes, Custodial care or Respite care facility

Hospitalization during the trial for a pre-planned surgical or medical procedure (one which is planned prior to entry in the trial **or** planned in advance and not related to the study procedure/drug), does not require reporting as a serious adverse event to the Sponsor.

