### **7.3.2 Serious adverse event reporting by Investigators**

It is important to distinguish between “serious” and “severe” adverse events, as the terms are not synonymous. Severity is a measure of intensity; however, an AE of severe intensity need not necessarily be considered serious. For example, nausea which persists for several hours may be considered severe nausea, but may not be considered an SAE. On the other hand, a stroke which results in only a limited degree of disability may be considered only a mild stroke, but would be considered an SAE. Severity and seriousness should be independently assessed when recording AEs on the CRF and SAEs on the SAE Report Form.

Adverse events classified by the treating investigator as **serious** require expeditious handling and reporting to sponsor in order to comply with regulatory requirements. Serious adverse events may occur at any time from the signing of the informed consent form through the 30-day follow-up period after the last trial treatment. Sponsor/sponsor representative must be notified of all SAEs, regardless of causality, within 1 day of the first knowledge of the event by the investigator.

To report an SAE, the SAE Report Form should be completed with the necessary information. All SAEs occurring from the signing of consent until 30 calendar days of last trial treatment must be reported to the Sponsor as SAEs on the SAE Report and followed until resolution (with autopsy report if applicable).

Deaths and other SAEs occurring >30 calendar days after last trial treatment that are deemed ‘possibly’ or ‘probably’ related to Tenalisib must be reported as SAEs on the SAE Report within 1 day of first knowledge of the event by the treating physician or research personnel (with an autopsy report if available). Deaths occurring >30 calendar days after last trial treatment and not attributed to trial treatment (e.g., disease progression) need not be reported as SAEs, but simply captured on the appropriate CRF.

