#### **7.4.5 Hospitalization, prolonged hospitalization, or surgery**

Any AE that results in hospitalization of >24 hours or prolonged hospitalization should be documented and reported as an SAE unless specifically instructed otherwise in this protocol. There are some hospitalization scenarios that do not require reporting as an SAE when there is no occurrence of an AE. (See [section 7.3](#))

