#### **7.4.8 New Cancers**

The development of a new primary cancer should be regarded as an AE and will generally meet at least one of the serious criteria. New primary cancers are those that are not the primary reason for the administration of the study treatment and have developed after the inclusion of the patient into the study. They do not include new lesions of the original cancer. Symptoms of metastasis or the new lesions itself should not be reported as an AE/SAE, as they are considered to be disease progression.

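### Protocol 7.3.1 lets relatedness decide whether a scheduled on-study admission for a procedure is reported as an SAE, against 7.3.2 and 7.4.5, so the all-cause Serious TEAE count may be too low

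*Protocol*

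**What the plan says.** Protocol 7.3.1 makes an event serious if, among other criteria, it "requires at least a 24-hour in-patient hospitalization or prolongation of existing hospitalization". That criterion carries no causality condition. The section later exempts certain admissions in a sentence with two limbs joined by *or*:

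- **First limb:** "Hospitalization during the trial for a pre-planned surgical or medical procedure (one which is planned prior to entry in the trial".
- **Second limb:** "planned in advance and not related to the study procedure/drug), does not require reporting as a serious adverse event to the Sponsor".

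Three other provisions bear on the same admissions:

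- Section 7.3.2 says the sponsor or its representative "must be notified of all SAEs, regardless of causality, within 1 day of the first knowledge of the event by the investigator".
- Section 7.4.5 says an AE that leads to a hospital stay of more than 24 hours is "reported as an SAE unless specifically instructed otherwise in this protocol". It then adds: "There are some hospitalization scenarios that do not require reporting as an SAE when there is no occurrence of an AE", and refers back to section 7.3.
- Section 7.4.6 has a pre-existing condition that worsens recorded as an AE or SAE, with no exception for scheduled treatment.

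SAP 10.6.2 tabulates Serious TEAEs and Related Serious TEAEs on separate lines, with the safety population as denominator. The first line is therefore meant to be all-cause.

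**The concern.** The second limb makes relatedness the test for whether a scheduled admission is reported as an SAE. Take a patient who develops a new condition on study and is booked in for elective surgery to treat it. If the investigator judges the matter unrelated to drug and study procedure, the sentence can be read as removing the admission from SAE reporting.

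Safety is the trial's only secondary objective, and SAEs are a named endpoint. A rule that can remove only unrelated events shifts the all-cause line and leaves the related line alone, so the related share of serious events would rise. The judgement behind it is a two-category investigator attribution in an open-label study (Protocol 3.4 and 7.2). An exempted admission also produces no SAE report through which the sponsor could look at that attribution again.

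**Working it through.** The documents state no SAE rate and no count of scheduled admissions, so there is no figure to reproduce. The check is a reading of the sections against each other, followed by arithmetic for scale.

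**Reading the text**

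1. The first limb already covers every procedure planned before entry. The second limb adds something only for procedures planned after entry. Read so that it has effect, it reaches admissions scheduled during the trial.
2. Its two conditions are advance planning, with no cut-off date, and lack of relation to drug or study procedure. Neither asks whether an AE led to the admission.
3. Section 7.3.2 excludes causality as a test for notification. The second limb uses it as one.
4. Section 7.4.5 describes the exempt scenarios as those without an AE, so an admission booked to treat an on-study AE would be reportable. But the same section gives way to specific instructions elsewhere in the protocol and points to 7.3. A site can treat the second limb as such an instruction. Two sites could follow the protocol and report the same admission differently.

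**Direction.** The limb covers only unrelated admissions. Related Serious TEAEs cannot change; all-cause Serious TEAEs can only fall.

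**Scale.** Inputs: 20 patients planned for Part 1 (SAP section 6) and the safety-set denominator (SAP 10.6.2). The rest is assumed.

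- Loss per affected patient who has no other reported serious TEAE: 1/20 = 5.0 percentage points. A patient with another serious TEAE causes no loss in the patient count.
- Illustration: suppose 4 patients truly have a serious TEAE, 2 of them related, and one unrelated case is exempted. The all-cause rate goes from 4/20 = 20% to 3/20 = 15%. The related share goes from 2/4 = 50% to 2/3 = 67%.
- Exact 95% intervals, for scale only: 5.7% to 43.7% for 4/20 and 3.2% to 37.9% for 3/20. The shift is small beside the imprecision at this sample size.
- Let q be the per-patient chance of such an admission. The chance that at least one of 20 patients is affected is 1 − (1 − q)^20. If affected patients have no other serious event, the expected loss is 100q points:
  - q = 1%: 0.18; 1 point
  - q = 2%: 0.33; 2 points
  - q = 5%: 0.64; 5 points
  - q = 10%: 0.88; 10 points

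The documents give no basis for choosing q, and zero is possible.

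**The case against.** The strongest answer is that the protocol already supplies the limit. Read with 7.4.5, the exempt admissions are those without an AE. An SAE must first be an untoward medical occurrence, which an elective procedure without an AE is not. The relatedness phrase can also be taken to describe the planned procedure rather than the attribution of an AE, and 7.2 treats toxicities as related unless there is a clear alternative explanation. This is a reasonable joint reading and probably the intended one. It does not remove the problem, because the deference clause in 7.4.5 leaves the opposite reading open and 7.3.1 itself has no AE condition.

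Other parts of the case against stand and limit the point:

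- A reader might infer that 7.3.1 exempts any hospitalization judged unrelated. It does not: only admissions for pre-planned surgical or medical procedures are covered.
- A reader might infer that the events disappear. They do not. Section 7.4 puts every AE on the AE CRF, 12.3 has the medical monitor review all AEs and SAEs regularly, and the SAP lists AEs and tabulates TEAEs by maximum grade. What is at risk is the seriousness classification and the prompt notification.
- Scheduled resection of a new primary cancer is a tempting example but a weak one. Section 7.4.8 says: "The development of a new primary cancer should be regarded as an AE and will generally meet at least one of the serious criteria". Such an event can also be serious as an important medical event without any admission. Elective surgery for a new, unrelated, non-malignant condition is the cleaner case.
- Safety is descriptive. No alpha, power or sample size depends on this.

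**Conclusion.** The conflict between 7.3.1 and both 7.3.2 and 7.4.5 is real and unresolved in the text. Following 7.3.1 as written can lower the all-cause Serious TEAE count and cannot change the related count.

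The documents do not support the stronger statement that the reported rate is too low. They give no number of scheduled admissions, so the supportable statement is that it may be too low by an unknown, possibly zero, amount.

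The figure of 5 points per patient rests on three assumptions:

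- The safety set is 20. The SAP refers to early closure and does not give the actual number; in general the loss is 100/N points.
- The patient has no other serious TEAE.
- A site that does not report the admission also leaves the AE unflagged as serious on the CRF. The exemption speaks of reporting to the sponsor, and 7.3.2 asks for seriousness to be assessed when AEs are recorded, so this last step is not certain.

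**What to change.** In Protocol 7.3.1, keep the second limb but replace its relatedness condition with: *and not performed because of an adverse event that began or worsened on study*. This brings the sentence into line with 7.3.2 and 7.4.5. Deleting the limb outright would over-correct, because elective procedures with no AE behind them, which 7.4.5 means to exempt, would then become reportable.

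SAP section 5.1 records that the study is closed, so new protocol wording cannot change what sites have already reported. Before database lock, also check for AEs with a scheduled admission of at least 24 hours that are not flagged serious, resolve each one, and state in the study report which rule was applied to the Serious TEAE tables.

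The cost is one protocol sentence, the matching line in any SAE completion guidance, and a short data review. The downside is a few more SAE reports and a slightly higher SAE rate.

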### **7.3.2 Serious adverse event reporting by Investigators**

It is important to distinguish between “serious” and “severe” adverse events, as the terms are not synonymous. Severity is a measure of intensity; however, an AE of severe intensity need not necessarily be considered serious. For example, nausea which persists for several hours may be considered severe nausea, but may not be considered an SAE. On the other hand, a stroke which results in only a limited degree of disability may be considered only a mild stroke, but would be considered an SAE. Severity and seriousness should be independently assessed when recording AEs on the CRF and SAEs on the SAE Report Form.

Adverse events classified by the treating investigator as **serious** require expeditious handling and reporting to sponsor in order to comply with regulatory requirements. Serious adverse events may occur at any time from the signing of the informed consent form through the 30-day follow-up period after the last trial treatment. Sponsor/sponsor representative must be notified of all SAEs, regardless of causality, within 1 day of the first knowledge of the event by the investigator.

To report an SAE, the SAE Report Form should be completed with the necessary information. All SAEs occurring from the signing of consent until 30 calendar days of last trial treatment must be reported to the Sponsor as SAEs on the SAE Report and followed until resolution (with autopsy report if applicable).

Deaths and other SAEs occurring >30 calendar days after last trial treatment that are deemed ‘possibly’ or ‘probably’ related to Tenalisib must be reported as SAEs on the SAE Report within 1 day of first knowledge of the event by the treating physician or research personnel (with an autopsy report if available). Deaths occurring >30 calendar days after last trial treatment and not attributed to trial treatment (e.g., disease progression) need not be reported as SAEs, but simply captured on the appropriate CRF.

The SAE report should be sent to the sponsor/sponsor representative via fax or e-mail within 24 hours of becoming aware of the event. The detailed SAE reporting process will be reviewed with sites during the site initiation visit as well as provided on the SAE report itself.. Transmission of the SAE report should be confirmed by the site personnel submitting the report. Follow-up information for SAEs and information on non-serious AEs that become serious should also be reported to Sponsor as soon as it is available; these reports should be submitted using the SAE Report Form.

Investigators must report SAEs and follow-up information to their responsible IRB/IEC according to the policies of the responsible IRB/IEC.

